Chronic Obstructive Pulmonary Disease (COPD) is characterized by increased mucus production, destruction of alveoli, and constriction of the conductive airways. This causes respiratory distress, impaired lung function, and a tendency towards frequent lower respiratory tract infections. COPD is a chronic and potentially life-threatening disease affecting approximately 380 million people worldwide (1). Acute Exacerbation of COPD (AECOPD) is the leading cause of death in COPD patients and survivors often suffer from mental disabilities such as anxiety and depression with substantial negative impact on self-rated health (2, 3).

The Global Initiative for Obstructive Lung Disease (GOLD) recommends inhaled corticosteroids (ICS) for patients with COPD with frequent and/or severe exacerbations and blood eosinophils $> 0.3 \times 10^9$ cells/L, and in those with $\geq 0.1 \times 10^9$ cells blood-eosinophils and recurrent exacerbations while on bronchodilators. The recommendations are derived from post-hoc-analyses from RCT's but yet no RCT has prospectively validated the recommendation (4, 5). Treatment with ICS is often prescribed in combination with inhaled Long-Acting Muscarinic Antagonist (LAMA) and Long-Acting Beta₂-Agonist (LABA). The effect of the treatment varies substantially among the patients studied, and in some cases, no improvement in the patients' condition is seen. Moreover, complications are seen, resulting from the use of ICS. Several studies have shown that treatment with ICS is associated with an increased risk of side effects such as pneumonia (6, 7), and in observational studies osteoporosis and diabetes (8, 9). Over-treatment with ICS is costly for both patients and society, associated with adverse events, and difficult to eradicate: approximately 70% of COPD patients continue to use ICS even when there is no obvious indication, and the effect is discrete or absent (10). The personal consequences of these complications for the patient have not been systematically addressed but are presumably of great importance to their quality of life.

Several clinical studies have shown that blood eosinophil count is a useful to predict treatment response to ICS in patients with COPD (11, 12). Airway inflammation plays a key role in AECOPD, which is mostly driven by neutrophilic inflammation, yet eosinophilic inflammation is the main driver in a subset of patients (13, 14). In COPD, ICS reduces the risk for AECOPD predominantly in the sub-population of with evidence of eosinophilic inflammation (15, 16). A personalized, eosinophil-guided, time-updated approach reduced systemic corticosteroid therapy during AECOPD (17). Yet, a personalized, eosinophil-guided approach to direct ICS in COPD patients with frequent AECOPDs has never been tested in a randomized trial. We wish to study this method with ICS in stable COPD to reduce ICS overtreatment and thus ICS-related adverse events.

AECOPDs can be prevented by prophylactic oral Azithromycin treatment. A small study (n=92) of showed that 12 months of Azithromycin treatment reduced the annual AECOPD among COPD patients classified as GOLD risk classes C or D, termed E in the lates GOLD version (21). A larger study (n=1142) confirmed these results; however, only 50% were in GOLD classes C or D and it is largely unknown how Azithromycin reduces exacerbation rates (22).

Long-term ICS treatment affects bacterial load in stable COPD, and lower eosinophil counts are associated with increased airway bacterial load (18, 19). Azithromycin exerts multiple effects on the structure and composition of the lower airway microbiota and has anti-inflammatory effects(20). No one has looked at the impact on the respiratory microbiota in patients receiving both treatments.

Thus, in the present four-arm facultative designed, randomized controlled, multicentre, parallel group study we have two aims: both to investigate whether an individualized and eosinophil-guided approach reduces ICS over-treatment and side effects, and whether oral low-dose prophylactic

Azithromycin 250 mg three times weekly reduces number of moderate-severe AECOPD and improves time alive and out of hospital.

2. Objectives

2.1 Clinical objectives

ICS

- Whether a strategy of eosinophil-guided¹ administration of ICS in COPD patients with GOLD class E and/or FEV₁ < 30% can lead to non-inferior² treatment responses to triple therapy (ICS/LABA/LAMA).
- Whether side effects³ due to ICS exposure can be reduced with the eosinophil-guided administration of ICS.

Azithromycin

- Whether the use of prophylactic low dose Azithromycin⁴ in COPD patients with GOLD risk E and/or FEV₁ < 30% can reduce moderate and severe exacerbations.

¹ Blood eosinophils are measured every 3rd month during the study. If blood-eosinophils < 0.3 x 10⁹ cells/L, ICS treatment will be paused for the next 3 months. If blood-eosinophils are ≥ 0,3 x 10⁹ cells/L, ICS treatment will be continued/resumed during the next 3 months.

² Unchanged number of COPD exacerbations or death from all cause within 365 days

³ New diagnosis of diabetes mellitus, change in HbA1c and antibiotic requiring infections

⁴ 250 mg Azithromycin three times weekly

2.2 Microbiota objectives

ICS

- Whether a strategy of eosinophil-guided administration of ICS in COPD patients with GOLD class E and/or $FEV_1 < 30\%$ leads to a change in (i) the respiratory microbiota abundance and diversity and (ii) the immunological profile in comparison to continuous triple therapy (ICS/LABA/LAMA).

Azithromycin

- Whether prophylactic low dose Azithromycin in COPD patients with GOLD class E and/or $FEV_1 < 30\%$ leads to changes in (i) the respiratory microbiota abundance and diversity and (ii) the immunological profile.

3. Hypotheses

ICS primary

- In COPD patients with GOLD class E and/or $FEV_1 < 30\%$, an eosinophil-guided administration of ICS treatment regimen is associated with no apparent loss of efficiency⁵.

ICS secondary

- In COPD patients with GOLD class E and/or $FEV_1 < 30\%$, eosinophil-guided administration of ICS will reduce the use of inhaled corticosteroids by $> 25\%$ ⁶.

⁵ Measured by "admissions with COPD exacerbation or death from all causes within 365 days

⁶ Measured by budesonide equivalent doses

- In COPD patients with GOLD class E and/or FEV₁ < 30%, eosinophil-guided administration of ICS will reduce the number of ICS related side effects.
- The respiratory microbiota have a composition of less "pathogenic" bacterial species in COPD patients with GOLD class E and/or FEV₁ < 30%, treated with the eosinophil-guided administration of ICS regimen compared to those treated with continuous triple therapy (ICS/LABA/LAMA) regimen.
- The complexity of the respiratory microbiota is lower among COPD patients with GOLD class E and/or FEV₁ < 30%, treated with continuous triple therapy (ICS/LABA/LAMA) regimen than among those treated with the eosinophil-guided administration of ICS regimen.
- The immunological profile of the upper airways changes in COPD patients with GOLD class E and/or FEV₁ < 30% treated with the eosinophil-guided ICS regimen compared to those treated with continuous triple therapy (ICS/LABA/LAMA) regimen.

Azithromycin primary

- In COPD patients with GOLD class E and/or FEV₁ < 30%, the use of low dose Azithromycin can result in a reduction in admissions with COPD exacerbation or death from all causes within 365 days" as compared to placebo.

Azithromycin secondary

- The difference in composition of the respiratory microbiota is substantial when COPD patients with GOLD class E and/or FEV₁ < 30% are treated with prophylactic low dose Azithromycin
- The immunological profile of the upper airways changes when COPD patients with GOLD class E and/or FEV₁ < 30% are treated with prophylactic low dose Azithromycin.

4. Methods

4.1 Study design

COPERNICOS is a 4-arm facultative designed, randomized controlled, multicentre, parallel group, double blinded, non-inferiority intervention study in participants with COPD (GOLD class E and/or $FEV_1 < 30\%$).

Participants will be randomly allocated to one of the following four treatment groups:

[figure not shown]

Figure 1: The four treatment groups (**Control** – **Active**)

1. Eosinophil "Control"/Azithromycin "Control" group:

- Azithromycin: participants are given placebo
- ICS: The participants are given the usual LAMA/LABA/ICS product in the usual dose.

2. Eosinophil "Active"/Azithromycin "Control" group:

- Azithromycin: placebo
- ICS: All participants will receive LABA/LAMA medication. The ICS medication will be switched on/off according to the most recent blood eosinophil count (at inclusion + every 3 months):
 - i. If blood eosinophil $\geq 0.3 \times 10^9$ cells/L, ICS is continued in usual dose next 3 months.
 - ii. If blood eosinophil $< 0.3 \times 10^9$ cells/L, ICS is discontinued.

3. Eosinophil "Control"/Azithromycin "Active" group:

- Azithromycin: 250 mg Azithromycin three times weekly.
- ICS: The participants are given the usual LAMA/LABA/ICS product in the usual dose throughout the entire project period

4. Eosinophil "Active"/Azithromycin "Active" group:

- Azithromycin: 250 mg Azithromycin three times weekly.
- ICS: All participants will receive LABA/LAMA medication. The ICS medication will be switched on/off according to the most recent blood eosinophil count (at inclusion + every 3 months):
 - i. If blood eosinophil $\geq 0.3 \times 10^9$ cells/L, ICS is continued in usual dose next 3 months.
 - ii. If blood eosinophil $< 0.3 \times 10^9$ cells/L, ICS is discontinued.

A microbiological and immunological study within the framework of the randomized study aims to investigate the respiratory microbiota and immunological profile in participants from the four randomized groups. A total of 40 participants from each group will participate in the sub-study and

will undergo tracheal aspirate collection and nasal swabs at baseline and 12 months follow-up. Collection of tracheal aspirates is a routine procedure at participating centres and serious complications are very rare. Nasal swab is not associated with any serious complications. Participants' data and laboratory specimens will be assigned a coded identification number to maintain participant confidentiality.

4.2 Recruitment

Participants for the trial will be recruited through advertisements and announcements on social media, in local newspapers, daily newspapers, and via the Danish Lung Association and its member magazine. Participants can contact trial staff by e-mail or telephone to receive the written participant information. Furthermore, patients at the outpatient clinic at each centre will be consecutively screened for eligibility for the trial. If a patient matches the criteria for the study, the patient will be invited to a screening meeting. The oral information session is given by a medical doctor who is duly qualified, including having knowledge of the trial to be able to provide information about it and answer any questions the subject may have. This meeting will take place in an undisturbed office.

Participants will be thoroughly screened for eligibility, and informed of the right to an assessor and companion at the first contact during an information meeting with trial staff. A 24-hour reflection period will be given to every participant, and informed consent will be obtained upon the signed consent declaration, provided that the participant will participate in the study. Only after receiving oral and written participant information, can informed consent be obtained. It is the primary investigator's responsibility at each centre to ensure that study personnel are trained, duly authorized, and competent to obtain informed consent. The consent to collect blood samples,

tracheal aspirates and nasal swabs to research biobank and future-research biobank is a separate part of the informed consent.

At recruitment health files regarding inclusion and exclusion criteria will be accessed for screening purposes before informed consent is obtained according to the Danish Health Care Act §46 (1). The following contact to possible participants will be at the next planned visit to the outpatient clinic.

During the project health files will be accessed by investigators for the following information:

- Medication
- Hospital admissions

If informed consent is obtained, the study sponsor, investigator, monitor, and the Danish Medicines Agency (Lægemiddelstyrelsen) will have access to health files, including electronic files, as part of the trial surveillance, quality control, etc.

Participants are allocated randomly via REDCap to one of the four arms; prior to randomization the inclusion and exclusion criteria will have been entered.

The azithromycin/placebo tablets are dispensed either as 500 mg tablets with a score line for splitting (patients are instructed to halve each tablet using the provided pill cutter, *or* as 250 mg capsules that should be swallowed whole without splitting. Patients will therefore be given very detailed instructions on the provided tablets or capsules, and on how to take the medication. The reason for having the medication in two different formulations is that the pharmacy producing the medication, for production reasons, has not been able to supply all the medication in the same formulation. Participants compliance to Azithromycin/placebo are monitored by both medicine diaries and leftover medicine returned at the 12-month examination. Blood eosinophil count will be monitored every 3 months from inclusion and participants will receive a phone call from a

nurse every 3 months to ensure that participants have taken ICS according to the physician's prescription and plan the next 3 months treatment according to protocol.

4.3 Inclusion criteria

- COPD (verified by a specialist in respiratory medicine + spirometry).
- GOLD class E anytime within the last 2 years (corresponding to $2 \geq$ AECOPD and/or ≥ 1 AECOPD leading to hospitalization during a 12 month period within the last 2 years) and/or $FEV_1 < 30\%$.
- Treatment for last 4 weeks including LAMA, LABA and ICS.
- Informed consent.

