Control group exacerbation/death: 0.3 (30%)

Expected maximum worsening >11% absolute (up to 0.41)

Sample size 444 (222 x 2)

A 1-sided superiority test for azithromycin.

Type 1 error limit (α) 2.5%, Power ($1-\beta$) of 80%. ($\alpha = 0.025$, $\beta = 0.2$)

Control group exacerbation/death: 0.3 (30%)

Expected effect: >10% absolute (up to 0.2)

Sample size 444 (222 x 2)

These two interventions will be published separately in two primary publications, but there will be adjustments in the main analysis to account for whether they received the other intervention. These two analysis teams (separate) will be blinded to an effect estimate of the other intervention.

40 participants from each group will participate in the microbiota sub-study.

Scheduled analyses of data (Interim analysis) will be assessed when half of the participants are recruited. These assessments will be made by the independent Data and Safety Monitoring Board (DSMB) on the two primary endpoints, and for the secondary endpoint “Death or “uncontrolled AECOPD tendency” within 365 days”. Data on primary and secondary power targets will be used for this purpose. DSMB will review the protocol, monitor the guideline, evaluate the trial concerning the recruitment of participants, participants' risk and, based on interim analyses, make recommendations to the investigators on whether to continue or cease the study. DSMB may at any time require an extraordinary interim analysis

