5.3 Exploratory

ICS

- Change in blood eosinophils from baseline to 365 days (eosinophilic trajectories)

⁷ ≥ 3 exacerbations within 12 months

- New diagnosis of diabetes mellitus within 365 days
- Change in HbA1c from baseline to 365 days
- Antibiotic-requiring infections within 365 days

ICS and Azithromycin

- Difference in respiratory microbiota abundance and diversity from baseline to 12 months between treatment arms
- Difference in immunological profile including cytokines and chemokines in the upper airways from baseline to 12 months between treatment arms
- Change in COPD-related quality of life (Based on COPD Assessment Test - CAT) from baseline to 365 days
- Number who progress to MRC -dyspnea score from < 3 to ≥ 3 anytime during follow-up (assessed every 3 months).
- Number of admission requiring non-invasive ventilation (NIV) treatment or admissions to intensive care within 365 days
- Mortality within 365 days

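### The only numeric definition of GOLD class E (Protocol section 4.3) has its inequality the wrong way round; it is probably a transposed operator, but it is an eligibility threshold and should be corrected

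*Protocol*

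**What the plan says.** Section 4.3 (Inclusion criteria) requires "GOLD class E anytime within the last 2 years" and then states in brackets what this corresponds to: "corresponding to $2 \geq$ AECOPD and/or ≥ 1 AECOPD leading to hospitalization during a 12 month period within the last 2 years". A separate route follows, "and/or $FEV_1 < 30" per cent, which does not depend on the exacerbation count.

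The objectives (section 2), hypotheses (section 3), study design (section 4.1) and scientific perspective (section 10) all describe the population by the class label and the FEV₁ route. None of them gives a count. The introduction, before section 2, describes the gap that the trial fills: "Yet, a personalized, eosinophil-guided approach to direct ICS in COPD patients with frequent AECOPDs has never been tested in a randomized trial".

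Section 4.2 (Recruitment) says that the inclusion and exclusion criteria are entered before participants are allocated through REDCap. It does not give the wording of the eligibility item.

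**The concern.** An inequality with the number on the left and the count on the right, 2 ≥ AECOPD, says that the count is at most two. Taken at face value, the limb meant to identify frequent exacerbators admits patients with no exacerbations. It also turns away some of those with the most.

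Eligibility criteria are audited as written. Under the literal text, a patient with no exacerbations would be compliant with this limb. A patient with many non-hospitalised exacerbations, who plainly belongs to the stated target population, could be recorded as a deviation. Because the criteria are entered before randomisation, the same symbol could also have been copied into the eligibility form, where it would matter more than it does on paper.

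**Working it through.** The plan gives no figure to reproduce here. The check is to enumerate the criterion and compare it with the rest of the document.

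**Inputs.** The count limb and the hospitalisation limb come from the bracket in section 4.3. The notation for other count thresholds comes from footnote 7, attached to the secondary endpoints. The intended population comes from the introduction.

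**Step 1: enumerate the count limb.** Let n be the number of AECOPD in a 12-month period, with none leading to hospitalisation.

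| n | As written (2 ≥ n) | As a lower bound (n ≥ 2) |
|---|---|---|
| 0 | met | not met |
| 1 | met | not met |
| 2 | met | met |
| 3 or more | not met | met |

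The two readings agree only at n = 2.

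**Step 2: add the hospitalisation limb.** This limb reads "≥ 1 AECOPD leading to hospitalization during a 12 month period within the last 2 years" and is joined by and/or. Under the literal reading, every patient with 0, 1 or 2 exacerbations already qualifies on the count. The hospitalisation limb could then change the result only for patients with 3 or more exacerbations in total. A criterion in which one hospitalised exacerbation counts for nothing until the total exceeds two makes little sense. With a lower bound, both limbs do work: one captures frequent exacerbations and the other captures severe ones.

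**Step 3: allow for the look-back window and the FEV₁ route.** The bracket refers to a 12-month period within the last 2 years. To be excluded under the literal text, a patient would need 3 or more exacerbations in every such 12-month period, no hospitalised exacerbation, and FEV₁ of at least 30%. Few patients are likely to fit that description. The wrongly admitting direction (n = 0 or 1) is therefore the broader of the two literal consequences.

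**Step 4: compare the notation.** Footnote 7 sets a lower bound on an exacerbation count with the operator before the number: "≥ 3 exacerbations within 12 months". The hospitalisation limb in section 4.3 does the same. The count limb is the exception.

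**Step 5: look for a correction elsewhere.** The other sections repeat the class label only. The stratification factor in section 5 (0-1 versus 2 or more hospital-requiring exacerbations in the past 12 months) is a different quantity and does not define the class.

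**Step 6: look for dependent figures.** The sample sizes in section 5 are stated from the control risk, the margin or effect, alpha and power. The bracket enters none of these, so correcting it changes no figure.

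**The case against.** The strongest reply is that the operative criterion is the class label and the bracket only glosses it. The label appears throughout the protocol, and the introduction ties it to the former classes C and D and to frequent exacerbations. Section 4.3 also requires COPD to be verified by a respiratory specialist. Such a reader would recognise the intended direction and would be unlikely to treat a patient without exacerbations as class E. The order of the symbols could also have arisen in converting the text, so the source PDF should be looked at before anything is amended.

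Most of this stands, and it limits the weight of the point. It does not remove it: the bracket is the only place where the class is given a number, and as written that number points the wrong way.

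A reader might go further and infer that low-risk patients have been enrolled. On that view the 30% control risk in section 5 would be out of reach, the azithromycin effect diluted and ICS non-inferiority made easier to show. The documents do not support this. It would require that the REDCap item carries the reversed operator, that staff followed it, and that low-risk patients were randomised as a result. The protocol shows none of the three. It also gives no event risk for patients below the class and no share of them, so any size put on such dilution would be invented.

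**Conclusion.** The bracket in section 4.3 is wrong as written. It sets an upper limit where its own second limb, the class label and the introduction all call for a lower one. It reverses the result at every count except exactly two, for patients who have no hospitalised exacerbation and do not enter through FEV₁.

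This is a drafting error in an eligibility threshold, not a flaw in the design. Its practical effect may be small or nil, and no sample-size or power figure moves. The conclusion assumes that the printed protocol shows the symbols in the order quoted and that the bracket is meant to describe the class it follows. Whether anyone was enrolled on the literal reading cannot be judged from the protocol.

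**What to change.** 1. Check the order of the symbols in the source PDF.
2. If it is as quoted, amend the first limb to a lower bound, ≥ 2 AECOPD, so that it runs in the same direction as the ≥ 1 limb and agrees with the class it defines.
3. Confirm that the eligibility item in REDCap uses the same direction.
4. Only if that item carries the reversed operator, review the qualifying exacerbation histories of participants already randomised.

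Steps 1 to 3 cost one symbol in an amendment and the inspection of one form item. Step 4 would be real work across several centres, since section 4.6 puts recruitment from 05JUL2021 to an expected 31AUG2025. That is why it should depend on what step 3 shows. No treatment, endpoint or sample-size statement needs to change.
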